•	and one-sided p-value for the superiority test will be presented for the comparison of daprodustat vs. rhEPO using the Cox Proportional Hazards model. The number and percentage of subjects with a MACE event and the number censored at the end of the study, the MACE incidence rate per 100 person-years, and the absolute rate difference per 100 person-years and associated two-sided 95% CI will be displayed with the results of the Cox proportional hazards regression model. To inform on the validity of the adjusted Cox proportional hazards model, the proportional hazards assumption will be assessed by plotting the logarithm of the negative logarithm of the estimated survivor function against the logarithm of time, for each treatment group. If the hazards are proportional, the lines should be approximately parallel. The hazard ratio, two-sided 95% CIs and one-sided non-inferiority and superiority p-values will be displayed on a forest plot together with supportive analysis results (i.e., excluding the Tipping Point Analysis). Time from Randomization to first adjudicated MACE event or end of trial will be evaluated using Kaplan-Meier (KM) methodology and displayed graphically for the comparison of daprodustat vs. rhEPO. A listing of all MACE events occurring during the study will be provided and will include treatment, site ID, unique subject ID, select demographic information, event type, event date,
Ma	and study day.
	del Results Interpretation
•	Non-inferiority will be achieved if the upper limit of the two-sided 95% CI for the hazard ratio is below the pre-specified non-inferiority margin of 1.25. For evaluation of MACE superiority, a principal secondary analysis, see Section 10.11.1.
Se	nsitivity Statistical Analyses
Tip	ping Point (Multiple Imputation) Analysis
•	Tipping point sensitivity analyses will be conducted under a range of missing data assumptions to determine how extreme assumptions need to be for non-inferiority conclusions to change. Assumptions about missing outcomes on the daprodustat and rhEPO arms will vary independently and will include scenarios where subjects with missing data on daprodustat have worse outcomes than subjects with missing data on rhEPO. Missing data that occurs before the end of the study (i.e., due to withdrawal from the study) will be imputed across a

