8.2.2.2. Planned Additional Secondary Safety Statistical Analyses

Additional CV Safety Endpoints

	condary Safety Statistical Analyses: Additional CV Safety Endpoints
	dpoint(s)
•	All-cause mortality, CV mortality, fatal or non-fatal MI, fatal or non-fatal stroke
	MACE or hospitalization for HF (recurrent events analysis)
	CV mortality or non-fatal MI
	All-cause hospitalization (see Section 10.6.4)
	All-cause hospital re-admission within 30 days (see Section 10.6.4)
	MACE or hospitalization for HF or thromboembolic events
	Hospitalization for HF
•	Thromboembolic events
Ло	del Specification
	Analysis of the endpoints above (except the recurrent event analysis) will be performed
	individually using an analysis model identical to that described for the co-primary MACE
	analysis for the evaluation of superiority, using the event dates defined in Section 10.6.4.
	Additionally, supportive summaries and analyses for the following endpoints will be generated
	including fatal events which are identified only through the death endpoint page and do not
	have a corresponding positively adjudicated endpoint event (see Section 10.6.4):
	 Stroke Thromboembolic events: Pulmonary Embolism
	For purposes of time-to-event models, subjects who have never been hospitalized will be right
•	censored (i.e., are still considered to be at-risk) for an all-cause hospital re-admission within 30
	days.
•	The recurrent event analysis of MACE or hospitalization for HF events will use the Prentice,
	Williams, Peterson (PWP) model [Prentice, 1981], based on the Cox proportional hazards
	model, to analyze the multiple event data. This model analyzes the time to first, second, etc.
	events while accounting for the correlation of events within an individual subject. Subjects are
	at risk for a k th event only if they survived a (k-1) st event. For the models described below, if
	there are not at least 15 k th events per arm, the treatment effect associated with the k th , $(k+1)$ th
	etc. events will not be estimated. All event times will be relative to randomization, as opposed
	to intra-event time (i.e. total times rather than gap times will be used).
	Three models will be used. The first model will estimate a common treatment effect, regardless
	of the number of events experienced by subjects. A second model will be run that allows the

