•	Summaries of adjudication details of all-cause mortality will include the number and percentage
•	of subjects by cause of death.
•	Summaries of adjudication details of MI will include the number and percentage of events by outcome of MI (fatal or non-fatal), type of MI, increased cardiac markers (y/n), ST segment
	classification [ST-elevation myocardial infarction (STEMI), non-ST-elevation myocardial infarction (NSTEMI), ECG not interpretable, ECG not available], and Q wave classification (Q wave MI, Non Q wave MI, ECG not interpretable, ECG not available).
•	Summaries of adjudication details of stroke will include the number and percentage of events
	by outcome of stroke (fatal or non-fatal), type of stroke (ischemic, hemorrhagic, or
	undetermined) and ischemic details (with/without hemorrhagic transformation) and location if
	hemorrhagic (intraparenchymal, intraventricular, subarachnoid, retinal, unknown location).
•	Summaries of adjudication details of heart failure will include the number of events by type:
	hospitalization for heart failure, heart failure requiring urgent ER/ED visit, heart failure requiring
	urgent office/practice visit, and fatal heart failure events identified by cause of death only.
•	Summaries of adjudication details of thromboembolic events will include the number and
	percentage of events by type of thromboembolic event (DVT, PE, VAT).
	 Summaries of PEs will include outcome of PE (fatal or non-fatal).
	 Summaries of VATs will include type of VAT (AV fistula, AV graft, central venous
	catheter, other), method of diagnosis (ultrasound/Doppler, AV imaging, CVC
	imaging, other), and treatment (thrombolytic therapy, thrombectomy, angioplasty,
	stent, surgical intervention, not specified).
•	The model results presentation for the endpoints above (except the recurrent event analysis)
-	will be identical to the co-primary MACE model results, with the single exception being the one-
	sided p-value presented will be for the test of superiority of daprodustat vs. rhEPO.
•	For the recurrent events analysis, hazard ratios, two-sided 95% CIs and one-sided chi-squared
	p-values associated with treatment effects (daprodustat vs. rhEPO) will be presented for the

200807

Secondary Safety Statistical Analyses: Additional CV Safety Endpoints

three models described above.

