8.2.4.2. Planned Adverse Event Safety Statistical Analyses

AESIs & PhRMA SPERT Adverse Event Analyses

Adverse events of special interest are described in Section 10.6.4.

Summaries of AESIs will include the number, percentage and rate per 100 person-years of subjects having at least one occurrence, the number of events, the number of subjects by number of occurrence, the characteristics of the AE (serious, drug-related, etc.), outcome, maximum intensity, time to first onset/worsening, and action taken summarized by treatment group. For each count, a subject will be summarized as follows:

- Serious/drug-related/severe/fatal: If any specific AE falls in the respective category, the subject will be counted in that category.
- Outcome: The subject will be counted within a category if there is at least one specific AE in that category.
- Maximum intensity: The specific AE with the maximum intensity will be counted for this purpose. For example, a subject will be counted in the 'severe' category if there is at least one specific AE with severe intensity. A subject will be counted in the 'moderate' category if there is at least one specific AE with moderate intensity and there is no specific AE with severe intensity.
- Time to first onset/worsening (days): The earliest of onset dates for the specific AE treatment start + 1

If the AE onset date/AE worsening and/or resolution date is missing or incomplete in the database for any occurrence of the specific AE, time to first onset/worsening will be left missing for the subject. These summaries of special interest AEs will be provided for those AEs classified as treatment emergent.

Cumulative incidence function (CIF) plots may be produced for each AESI summarizing the time to first occurrence of the AESI by treatment group. If there are less than 20 subjects total for both the daprodustat and rhEPO arm, then these plots will not be created. Competing risks for the AESI cumulative incidence plots include:

AE of Special Interest (Event of interest)	Competing Risk Events
Thrombosis and/or tissue ischemia secondary	Death due to any cause prior to the AESI
to excessive erythropoiesis	
Cardiomyopathy	Death due to any cause prior to the AESI
Pulmonary artery hypertension	Death due to any cause prior to the AESI
Cancer-related mortality and tumor progression	All other non-cancer-related death prior to the
and recurrence	AESI (use death date as the competing risk
	date)

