• •	• Calculated as the latest randomized treatment dose stop date, for subjects who have a non- missing treatment start date. Note that this date could come from a randomized treatment exposure record with a missing or partial dose stop date if the associated dose start date for that exposure record is on or after the last non-missing randomized treatment dose stop date.			
	 '31' will be used for the day and 'Dec' will be used for the month, unless the study completion or withdrawal date also occurs in the same year; in this case, the study completion or withdrawal date will be used. Missing day, month and year: The study completion or withdrawal date will be used only for subjects 			
	who have a non-missing treatment start date.			
End	of Treatment Value			
	 Only defined for subjects with a non-missing treatment start date Hgb, iron, transfusion and PRO parameters: the latest value on or before the treatment stop date + 1 day. Blood pressure, central laboratory, and vital signs parameters: the latest value on or before the last non-zero dose date + 1 day. 			
Stud	ly Completion/Withdrawal Date			
	 Date of withdrawal for subjects withdrawing (i.e., subjects who actively withdraw or are deemed lost to follow-up) from study or date of completion of study for subjects who complete the study. If the date of study withdrawal entered in the eCRF is before the last study contact date, the last study contact date will be used as the study withdrawal date for analysis. 			
	 Note: Subjects who die while on study are considered as having completed the study 			
	 The eCRF allows for the possibility of missing or partial dates to be recorded for the study completion/withdrawal date on the Study Conclusion form (i.e., missing day, or day and month, or day and month and year). In such a case, or in case of subjects who are missing a Study Conclusion form, the following conventions will be applied in order to impute a study completion/withdrawal date: Missing day: 			
	 The last day of the month will be used, unless the last study contact date also occurs in the same month; in the case, the last study contact date will be used. 			

200807

the last study contact date also or last study contact date will be use	Dec' will be used for the month, unless ccurs in the same year; in this case, the ed.
 Missing day, month and year: The last study contact date will be 	
Planned/Actual Visit Dates	
Planned/actual visit dates will be defined as follow	

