 First event incidence rate (per 100 person years) = (100 * number of subjects with at least 1 event) / first event person years
• First event absolute rate difference (per 100 person years) = daprodustat incidence rate (per 100 person years) – rhEPO incidence rate (per 100 person years)
Evaluation Time Periods for CV Endpoints
Time Period for Follow-up of Cardiovascular Endpoints
The period for capturing CV safety endpoints begins at randomization. The end of this time period is the date of study completion/withdrawal, with the exception that if a death has been reported in the clinical database after this time, then the death will be included in the analysis.
Any endpoints that occurred before the start of this time period are considered to be prior to the time period for follow-up of cardiovascular safety events, and any endpoints that occurred after the end of this time period are considered to be post the time period for follow-up of cardiovascular safety endpoints.
Time Period for Vital Status
The period for capturing vital status begins at the date of randomization. The end of this time period is defined as follows:
For all subjects known to have died, use the date of death
• For all subjects who complete the study, use the study completion date (see Section 10.6.1)
• For all subjects who withdraw from the study, but vital status has been ascertained, and are known to have not died – use the latest date last known to be alive. If vital status has not been ascertained following study withdrawal, use the study withdrawal date
Any endpoints that occurred before the start of this time period are considered to be prior to the time period for vital status, and any endpoints that occurred after the end of this time period are considered to be post the time period for vital status.
Time Period for On-treatment Cardiovascular Endpoints
The period for capturing on-treatment CV safety endpoint events begins at the treatment start date The end of this time period is defined as follows:
 For subjects whose last non-zero dose date is missing and who took randomized treatment, use date of study withdrawal/completion
 For subjects continuing on study past the last non-zero dose date +28 days, use (last non-zero dose date + 28)
 For subjects whose study withdrawal/completion date is on or before (last non-zero dose date +28), use date of study withdrawal/completion

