 hazards a estimated dialysis ty Should th methods 	on the validity of the adjusted Cox proportional hazards model, the proportional assumption will be assessed by plotting the logarithm of the negative logarithm of the l survivor function against the logarithm of time, for each treatment group, region and ype. If the hazards are proportional, the lines should be approximately parallel. ere be evidence of a violation of the proportional hazards assumption, the following may be considered:		
o Use c	 Use of a stratified Cox proportional hazards model (including prognostic factors in a 		

STRATA statement in PROC PHREG, rather than in the MODEL statement)							
Endpoint(s) Time to first event endpoints with death as a competing risk							
Analysis							
and one of then addit	 If there is a notable difference between one or both of all-cause mortality and non-CV mortality, and one or more of the secondary CV endpoints that do not include death as a component, then additional analysis methods to address competing risks may be pursued such as: Fine & Gray's Subdistribution Hazards (Fine, 1999) 						

200807

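### For additional CV endpoints that do not include all-cause death, the inherited Kaplan-Meier plot censors deaths not counted as the endpoint and so overstates cumulative incidence; an Aalen-Johansen plot should be added

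*SAP*

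**What the plan says.** Section 8.2.2.2 lists the additional secondary CV endpoints, beginning with "All-cause mortality, CV mortality, fatal or non-fatal MI, fatal or non-fatal stroke". Leaving aside the recurrent-event analysis, it states that their results presentation "will be identical to the co-primary MACE model results, with the single exception being" that the p-value is for superiority. The presentation being copied, in Section 7.2.2, contains this item: "Time from Randomization to first adjudicated MACE event or end of trial will be evaluated using Kaplan-Meier (KM) methodology and displayed graphically". Table 10 marks a statistical-analysis figure for each of the eight endpoints that lack all-cause death: CV mortality, MI, stroke, CV mortality or non-fatal MI, all-cause hospitalization, 30-day re-admission, heart failure hospitalization and thromboembolic events.

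The censoring rule comes from two other places. Section 10.6.4.1 says of CV follow-up: "The end of this time period is the date of study completion/withdrawal", with later-reported deaths added. Section 10.6.1 notes: "Subjects who die while on study are considered as having completed the study". The general definitions in 10.6.4.1 recognise only two outcomes, event time or censoring time.

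Competing risks appear twice elsewhere. In Section 8.2.4.2, "Cumulative incidence function (CIF) plots may be produced for each AESI summarizing the time to first occurrence", with death as the competing event. In Section 10.12.1, for first-event endpoints that death can preclude, "additional analysis methods to address competing risks may be pursued such as" the Fine and Gray model, provided a notable difference is seen.

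**The concern.** For MACE, every death is an event, so no death is censored and 1-KM estimates the proportion with an event. Once the same plot is used for MI or hospitalization, a subject who dies of something else is censored and treated as still able to have the event later. The curve then describes a setting in which such deaths do not occur, and it lies above the proportion of subjects who actually reach the endpoint.

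These are safety figures, and readers commonly take absolute risk from them. There is also an inconsistency within the report. Thrombosis as an AESI may be shown as cumulative incidence with death competing, while adjudicated thromboembolic events would be shown by Kaplan-Meier. Overlapping clinical events could then appear on two different absolute-risk scales.

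**Working it through.** **Step 1: what happens to a death.** A subject who dies on study is a completer (10.6.1). CV follow-up ends at completion (10.6.4.1). With only event and censored states defined, a death that is not itself the endpoint becomes a censoring in the plot required by 8.2.2.2 and 7.2.2.

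**Step 2: inputs.** The SAP states no cumulative incidence, event rate or mortality rate for these endpoints, so there is no figure of its own to reproduce. All rates below are assumptions. Let λ be the endpoint hazard, μ the hazard of death not counted as the endpoint, and t the time in years, with constant hazards.

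- With deaths censored: 1-KM(t) = 1 - exp(-λt)
- With death as a competing event: CIF(t) = λ/(λ+μ) × [1 - exp(-(λ+μ)t)]

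**Step 3: base case.** λ = 0.03, μ = 0.08, t = 3.

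- 1-KM = 1 - exp(-0.09) = 0.0861
- CIF = 0.03/0.11 × [1 - exp(-0.33)] = 0.0767
- Gap 0.0094, ratio 1.12

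Varying μ, with λ = 0.03 and t = 3:

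| μ per year | 1-KM | CIF | Gap (points) | Ratio |
|---|---|---|---|---|
| 0.06 | 8.61% | 7.89% | 0.72 | 1.09 |
| 0.08 | 8.61% | 7.67% | 0.94 | 1.12 |
| 0.10 | 8.61% | 7.45% | 1.15 | 1.155 |

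**Step 4: dependence on the event rate.** At μ = 0.10 and 3 years:

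| λ per year | 1-KM | CIF |
|---|---|---|
| 0.01 | 3.0% | 2.6% |
| 0.06 | 16.5% | 14.3% |
| 0.10 | 25.9% | 22.6% |
| 0.60 (a frequent event, as hospitalization might be) | 83.5% | 75.2% |

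Over λ from 0.01 to 0.60, μ from 0.05 to 0.15 and t from 2 to 4 years, the relative overstatement runs from 4% to 33% and the absolute gap from 0.1 to 14.9 points. A simulation of 400,000 subjects at λ = 0.06, μ = 0.10 and 3 years gave 16.48% for 1-KM and 14.31% for Aalen-Johansen. The formulas give 16.47% and 14.30%.

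**Step 5: does it need a mortality difference between arms?** No. Steps 3 and 4 each concern a single arm. Two arms with the same λ and μ show the same overstatement.

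**Step 6: what a mortality difference does.** Take λ = 0.06 in both arms, and μ = 0.12 against 0.10. At 3 years 1-KM is 16.5% in both arms and the curves coincide. The CIFs are 13.9% and 14.3%.

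**The case against.** The strongest reply is that no planned number is wrong. The tabulated absolute measures for these endpoints are counts and percentages of subjects with events, and incidence rates and rate differences per 100 person-years. None is read off 1-KM, and no landmark Kaplan-Meier percentage is planned. The Cox hazard ratio is a cause-specific one and remains valid as such. All of this stands. The problem is confined to absolute risk as read from the figures.

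A reader might infer that the curves distort the comparison between arms when mortality differs. The documents and the arithmetic do not support that. Under the same independent-censoring assumption as the Cox model, Kaplan-Meier tracks the cause-specific hazard, and in Step 6 it is the CIF that separates the arms. Cumulative incidence therefore has an interpretive cost of its own: an arm with more deaths can appear to have slightly fewer events.

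It can also be said that the sponsor did consider competing risks, since 8.2.2.2 refers to Appendix 12. That is true, and Fine and Gray is given there only as an example. The trigger is loosely worded: it sets mortality against the CV endpoints and is not clearly a between-arm difference in mortality. On either reading the clause is optional, depends on the results and leaves the planned plots as they are. The AESI plots are likewise optional and are dropped when fewer than 20 subjects have the event, so they show only that the method is foreseen in this SAP.

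**Conclusion.** The point holds as a limited one. For the eight endpoints without all-cause death, the planned plot overstates cumulative incidence whenever anyone dies without the endpoint. The direction is certain under the plan's censoring rule. The size is not, because it rests wholly on assumed constant hazards. At an event hazard of 0.03 and death hazards of 0.06 to 0.10 per year, it is about 9% to 15.5% relative at 3 years, or 0.7 to 1.15 points. It is smaller in points for rare endpoints and larger for frequent ones.

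Three wider readings should be avoided.

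- The issue is not one of non-fatal endpoints. MI and stroke include fatal events, and adjudicated fatal pulmonary embolism counts as a thromboembolic event. Only deaths not counted as the endpoint are censored.
- The SAP gives no mortality rate, so it does not establish that the bias is large in this population.
- No confirmatory result is in doubt. MACE, the principal secondary composites, the triple composite and all-cause mortality include every death, and the endpoints at issue are tested only nominally.

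**What to change.** Add one sentence to Section 8.2.2.2. For each endpoint without all-cause death, the absolute-risk figure will be an Aalen-Johansen cumulative incidence plot by arm, with death not counted as the endpoint as the competing event (non-CV death for the two CV-mortality endpoints), produced whatever the results show. The Kaplan-Meier plot may be kept beside it, labelled as a cause-specific display. The Cox models, hazard ratios, person-year rates and tests do not change.

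The cost is a few extra figures using a method already foreseen for AESIs. Because cumulative incidence also reflects mortality differences, each plot should carry a note that it is to be read with the cause-specific hazard ratio and the mortality results.

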8.2.3. Exploratory Safety Analyses

8.2.3.1. Overview of Planned Exploratory Safety Analyses

Table 11 provides an overview of the planned exploratory safety analyses.

Table 11 Overview of Planned Exploratory Safety Analyses

Endpoint				olute		Cha	ange fro	m Base	line
	Population	Sum	Summary		vidual	Sum	mary	Indiv	idual
		Т	F	F	L	Т	F	F	L
BP and BP Medication (Changes								
SBP, DBP and MAP by visit	ITT	Ir	ncluded w	/ith BP se	econdary	analyse	s (Sectio	on 8.2.2)	1
SBP, DBP, and MAP change from baseline to last record prior to change in BP medications ¹	ITT					Y			
Number of BP medications per subject by visit ¹	ITT	Y							
CFB in number of BP medications per subject by visit ¹	ITT					Y			
Number (%) of subjects who had no change, an increase or a decrease in dosage or number of BP medications from baseline by visit ¹	ITT	Y							
Lipid Parameters									
Lipid parameters by visit (TC, LDL-C, HDL- C)	ITT	Y	Y			Y			

NOTES:

• T = Table, F = Figure, L = Listing, Y = Yes display generated.

• Summary = Represents TFL related to any summaries (i.e. descriptive statistics) of the observed raw data.

• Individual = Represents FL related to any displays of individual subject observed raw data.

[1]: Summary will include on-treatment BP values or BP medications taken while the subject was on treatment only.

200807

